Main objectives and endpoints	
  
 Objectives	Endpoints	
   
 Primary objective	Primary endpoints	
 
 To demonstrate non-inferiority of tralokinumab versus placebo with respect to immune responses to concomitantly administered vaccines.	 
 
Positive anti-tetanus response at Week 16 (3-fold IgG increase compared to Week 12 if IgG ≤1.0 IU/mL at Week 12; or IgG ≥2.5 IU/mL if IgG >1.0 IU/mL at Week 12)
 
Positive anti-meningococcal response at Week 16 (IgG ≥3.0 mcg/mL with at least a 3-fold increase compared to Week 12)
 
 	
 
 Secondary objective	Secondary endpoints	
 
 To evaluate efficacy of tralokinumab concomitantly administered with vaccines.	 
 
Investigator Global Assessment (IGA) score of 0 (clear) or 1 (almost clear) at Week 16
 
At least 75% reduction in Eczema Area and Severity Index (EASI75) at Week 16
 
 	
 
 Additional secondary objective	Additional secondary endpoints	
 
 To evaluate safety and tolerability of tralokinumab concomitantly administered with vaccines.	 
 
Number of adverse events (AEs)
 
Presence of anti-drug antibodies
 
 	
  
	Objectives	Endpoints	Primary objective	Primary endpoints	To demonstrate non-inferiority of tralokinumab versus placebo with respect to immune responses to concomitantly administered vaccines.	
 
Positive anti-tetanus response at Week 16 (3-fold IgG increase compared to Week 12 if IgG ≤1.0 IU/mL at Week 12; or IgG ≥2.5 IU/mL if IgG >1.0 IU/mL at Week 12)
 
Positive anti-meningococcal response at Week 16 (IgG ≥3.0 mcg/mL with at least a 3-fold increase compared to Week 12)
 
	Secondary objective	Secondary endpoints	To evaluate efficacy of tralokinumab concomitantly administered with vaccines.	
 
Investigator Global Assessment (IGA) score of 0 (clear) or 1 (almost clear) at Week 16
 
At least 75% reduction in Eczema Area and Severity Index (EASI75) at Week 16
 
	Additional secondary objective	Additional secondary endpoints	To evaluate safety and tolerability of tralokinumab concomitantly administered with vaccines.	
 
Number of adverse events (AEs)
 
Presence of anti-drug antibodies
 

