### Panel 5: Identification of IMPs (vaccines)

Investigational medicinal product	Dosage form and pack size	Active ingredient and concentration	Source
Tdap vaccine	Suspension for injection in 0.5 mL single-dose pre-filled syringes.	
Combined diphtheria, tetanus, acellular pertussis (adsorbed) vaccine.
 
The vaccine contains diphtheria toxoid, tetanus toxoid, and 3 purified pertussis antigens (pertussis toxoid, filamentous haemagglutinin, and pertactin) adsorbed onto aluminum salts. The final vaccine is formulated in saline.
 
Each 0.5 mL dose is formulated to contain 5 limit of flocculation (Lf) of tetanus toxoid, 2.5 Lf of diphtheria toxoid, 8 mcg of inactivated pertussis toxoid, 8 mcg of filamentous haemagglutinin, and 2.5 mcg of pertactin (69 kDa outer membrane protein).
	Commercially available; supplied by the CMO.
Meningococcal vaccine	Solution for injection in 0.5 mL single-dose vials.	
Meningococcal (groups A, C, Y and W-135) polysaccharide diphtheria toxoid conjugate vaccine.
 
Each 0.5 mL dose of vaccine is formulated in sodium phosphate buffered isotonic sodium chloride solution to contain 4 mcg each of meningococcal A, C, Y and W-135 polysaccharides conjugated to approximately 48 mcg of diphtheria toxoid protein carrier.
	Commercially available; supplied by the CMO.

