### 14.3.5 Analysis of primary endpoints

Positive anti-tetanus response at Week 16 (3-fold IgG increase compared to Week 12 if  $\text{IgG} \leq 1.0$  IU/mL at Week 12; or  $\text{IgG} \geq 2.5$  IU/mL if  $\text{IgG} > 1.0$  IU/mL at Week 12) and positive anti-meningococcal response at Week 16 ( $\text{IgG} \geq 3.0$  mcg/mL with at least a 3-fold increase compared to Week 12) are binary endpoints. The difference in response rates between treatment groups will be calculated using the Mantel-Haenszel estimate of the risk difference stratified by baseline disease severity (IGA 3 or 4) together with the 95% CI. Non-inferiority of tralokinumab will be demonstrated if the lower limit of the 95% CI is greater than -25%.

The primary endpoints will be analysed for FAS and the per protocol set; the per protocol analysis will be considered the primary analysis. Analyses will be based on observed data; hence, missing data will not be imputed.

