SCORAD	Scoring Atopic Dermatitis
SCORAD50	At least 50% reduction in SCORAD score
SCORAD75	At least 75% reduction in SCORAD score
SOC	system organ class

Tdap	Tetanus, diphtheria and acellular pertussis
ULN	upper limit of normal
VAS	visual analogue scale

4 Introduction

The statistical analysis will be performed as outlined in the clinical trial protocol.

This statistical analysis plan is prepared before the unblinding of the trial and supplements the clinical trial protocol, which otherwise describes the originally planned statistical analyses of all endpoints in an intended exhaustive manner. The statistical analysis plan contains a more technical and detailed elaboration of some points related to the implementation of the statistical analysis already described in the clinical trial protocol.

In addition, the Statistical Analysis Plan includes supplementary statistical analyses and aspects that are introduced after the protocol.

Definition of vaccine response:

1. The definition and calculation of positive meningococcal response has been specified.

New analysis for the continuous other endpoints:

2. Analysis of a new tertiary estimand ('composite') for the continuous other endpoint 'Change from baseline to Week 16 in EASI score' is introduced. Analysis apply non-responder imputation for subjects who receive rescue medication.
3. A repeated measurements analysis of the percentage change from baseline in EASI score from baseline to Week 16 has been added.

The per protocol analysis set:

4. The definition of the per protocol analysis set as stated in the protocol has been updated with regards to handling of systemic rescue medication, baseline disease severity related to the EASI status and visit interval between administration of the vaccine and measurement of the vaccine response.

5 Trial analysis sets

The trial analysis sets are defined in the protocol and the following modifications to the analysis sets are introduced.

All subjects randomised to treatment who were exposed to IMP (tralokinumab/placebo) are included in the full analysis set and will be analysed for efficacy up to Week 16 (Visit 11). For subjects not exposed to IMP (tralokinumab/placebo), the decision to withdraw can't be biased by knowledge of the assigned treatment due to the blinding. This definition of the full analysis set implements the consideration mentioned in the protocol regarding special excluded cases with reference to ICH E9, Section 5.2.1.

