6.6 Vaccine responders

As stated in the protocol, a positive anti-tetanus response is defined as a 3-fold IgG increase at Week 16 compared to Week 12 if $\text{IgG} \leq 1.0 \text{ IU/mL}$ at Week 12; or $\text{IgG} \geq 2.5 \text{ IU/mL}$ if $\text{IgG} > 1.0 \text{ IU/mL}$ at Week 12.

As stated in the protocol, a positive anti-meningococcal response is defined as at least a 3-fold increase in specific IgG at Week 16 compared to Week 12.

The anti-meningococcal response is measured in separate assays against four individual meningococcal serogroup antigens, including serogroup A, C, W-135 and Y. To assess the vaccine response against a serogroup antigen a measurable specific IgG titer against that antigen at both week 12 and week 16 should be available. Subjects with a visit interval between Week 12 and Week 16 of ≥ 56 days are excluded from the analysis due to a too long interval between administration of the vaccine and measurement of the vaccine response.

In order to reduce the impact of missing data on the calculation of responders to the meningococcal vaccination the following will be applied:

- If data are available for 4 out of the four antigens, then the subject should be a responder against at least 3 of the antigens
- If data are only available for 3 out of the four antigens, then the subject should be a responder against these 3 antigens
- If data are only available for 2 out of the four antigens, then the subject should be a responder against these 2 antigens
- If data are only available for 1 out of the four antigens, then the subject should be a responder against this 1 antigen

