6.8.4 Laboratory data

Laboratory data will be summarised and listed.

For the laboratory values, if the value is below the lower limit of quantification, half of the lower limit will be used for quantitative summaries. If the value is above the upper limit of quantification, the upper limit value will be used.

If more than laboratory value is reported for the same visit, the latest value will be used in summary statistics and analyses.

Potentially clinically significant values will be defined as displayed in [Table 4](#).

Table 4: Potentially clinically significant biochemistry and haematology values

Protocol lab parameter	SI unit	PCS low	PCS high
Biochemistry			
Sodium	mmol/L	< 129 mmol/L, < 125 mmol/L	> 160 mmol/L
Potassium	mmol/L	< 3 mmol/L, < 2.5 mmol/L	> 6.5 mmol/L, > 7.5 mmol/L
Creatinine	umol/L	N/A	> 1.5xULN, > 3xULN
Calcium	mmol/L	< 1.9 mmol/L	> 3.0 mmol/L, > 3.5 mmol/L
Alkaline phosphatase	U/L	N/A	> 3xULN
Aspartate aminotransferase	U/L	N/A	> 3xULN, > 5xULN, > 10xULN, > 20xULN
Alanine aminotransferase	U/L	N/A	> 3xULN, > 5xULN, > 10xULN, > 20xULN
Bilirubin	umol/L	N/A	> 2xULN
Cholesterol	mmol/L	N/A	> 6.2 mmol/L
LDL cholesterol	mmol/L	N/A	> 4.1 mmol/L, > 4.9 mmol/L
HDL cholesterol	mmol/L	N/A	> 1.6 mmol/L
Triglycerides	mmol/L	N/A	> 2.3 mmol/L, > 5.6 mmol/L
Glucose (non-fasting)	mmol/L	< 3.9 mmol/L	>11.1 mmol/L
Haematology			
Haemoglobin	g/L	<110 g/L, < 80 g/L	> 185 g/L for male, > 165 g/L for female
Neutrophils, absolute count	10 ⁹ /L	< 1.5×10 ⁹ /L, < 1.0×10 ⁹ /L, < 0.5×10 ⁹ /L	N/A
Lymphocytes, absolute count	10 ⁹ /L	< 1.0×10 ⁹ /L, < 0.5×10 ⁹ /L	> 5.0×10 ⁹ /L
Monocytes, absolute count	10 ⁹ /L	< 0.1×10 ⁹ /L	> 0.8×10 ⁹ /L
Eosinophils, absolute count	10 ⁹ /L	N/A	> 1.5, > 5.0
Basophils, absolute count	10 ⁹ /L	N/A	> 0.2
Thrombocytes	10 ⁹ /L	< 100×10 ⁹ /L, < 30×10 ⁹ /L, < 10×10 ⁹ /L	> 450×10 ⁹ /L

Abbreviations: HDL = high density lipoprotein; LDL = low density lipoprotein; N/A = not applicable; PCS = potentially clinically significant; ULN = upper limit of normal (i.e., upper limit of normal reference range).

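### SAP 6.6 leaves out the protocol's IgG ≥3.0 mcg/mL condition for a meningococcal response without declaring the change, and does not define a measurable titre

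*SAP*

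**What the plan says.** The protocol defines the endpoint in the synopsis as "Positive anti-meningococcal response at Week 16 (IgG ≥3.0 mcg/mL with at least a 3-fold increase compared to Week 12" and repeats both conditions in Panel 3, section 12 and section 14.3.5. Section 12 ties the criteria to what the assays themselves treat as a positive response. The protocol gives no rule for combining the four serogroups.

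SAP 6.6 gives only the fold-rise: "As stated in the protocol, a positive anti-meningococcal response is defined as at least a 3-fold increase in specific IgG at Week 16". The anti-tetanus sentence just above it keeps all its thresholds. SAP section 4, which lists what is new since the protocol, says only "The definition and calculation of positive meningococcal response has been specified".

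SAP 6.6 then adds a serogroup rule. Each antigen has its own assay and is assessed only if "a measurable specific IgG titer against that antigen at both week 12 and week 16 should be available". The pass mark depends on how many antigens are available: 3 of 4, 3 of 3, 2 of 2 or 1 of 1. For two, for example, "If data are only available for 2 out of the four antigens, then the subject should be a responder against these 2 antigens".

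The only below-limit rule in the SAP is in section 6.8.4 on safety laboratory data: "if the value is below the lower limit of quantification, half of the lower limit will be used for quantitative summaries". For the primary endpoints, protocol 14.3.5 states "Analyses will be based on observed data; hence, missing data will not be imputed".

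**The concern.** Two documents that should agree give different responder definitions for a primary endpoint, and the SAP's version claims the protocol as its source. A programmer must work from SAP 6.6, because only that section says how to combine serogroups, and would therefore leave out the 3.0 condition. Protocol 14.3.10 asks for changes to the planned analysis to be described and justified. The SAP does this for its changes to the per protocol set but not here.

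The undefined word adds a second source of divergence. A below-limit titre is an observed result. If it is treated as not measurable it becomes missing, and the pass mark changes with it. Two programmers could then derive different responders from the same data.

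**Working it through.** **The plan's own figures.** These reproduce and are not in dispute. Inputs from protocol 14.1: 80% response in both arms, margin -25%, 160 in the per protocol set (80 per arm), one-sided 2.5%. Power = Φ(0.25/√(2×0.8×0.2/80) − 1.96) = 97.7%, against a stated 98%. With IGA 0/1 at 94.8% and EASI75 at 98.1% (100 per arm), power for all four hypotheses is 0.977×0.977×0.948×0.981 ≈ 88.8%, against a stated figure of about 89%.

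**Effect of the missing condition.** Let b be Week 12 IgG for a serogroup, and apply both conditions per serogroup (an assumption; see the fix).
- SAP: Week 16 IgG must reach 3b.
- Protocol: Week 16 IgG must reach max(3.0, 3b).
- If b ≥ 1.0, then 3b ≥ 3.0 and the two rules are the same.
- If b < 1.0, they differ for Week 16 values from 3b up to just under 3.0. The SAP accepts these and the protocol does not.
- Example: 0.2 to 0.7 mcg/mL on all serogroups is a 3.5-fold rise, so a responder under the SAP. Since 0.7 < 3.0, it is a non-responder under the protocol.

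With the available serogroups fixed, extra serogroup responses can only turn a non-responder into a responder.

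**Effect of the undefined word.** Suppose measurable excludes below-limit results:

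| Subject | Below-limit treated as missing | All four counted |
|---|---|---|
| Responds on A (from below limit), C and Y; W-135 measurable, no response | 2 of 3: non-responder | 3 of 4: responder |
| Two serogroups below limit at both visits; other two respond | 2 of 2: responder | 2 of 4: non-responder |
| All four below limit at Week 12, strong rise | no result | can be assessed |

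**Can a sign be given?** Two assumed scenarios, with independent serogroups calibrated so that 3 of 4 gives 80%. This needs a per-serogroup rate p = 0.788, with p³ = 0.489 and p² = 0.620.
1. Each serogroup is dropped with probability 0.10, unrelated to response. The chances of 4, 3, 2 or 1 remaining are 0.6561, 0.2916, 0.0486 and 0.0036. Rate ≈ 0.6561×0.80 + 0.2916×0.489 + 0.0486×0.620 + 0.0036×0.788 = 0.700. Power = Φ(0.25/√(2×0.700×0.300/80) − 1.96) ≈ 93.2%.
2. Only non-responding serogroups are dropped, half of them (0.212/2 ≈ 10.6% of titres). No responder is lost. Non-responders scored as responders: 6p²(0.212)²×0.25 + 4p(0.212)³×0.125 ≈ 0.042 + 0.004 = 4.6%. Rate ≈ 0.846. Power = Φ(0.25/√(2×0.846×0.154/80) − 1.96) ≈ 99.2%.

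Similar shares of dropped titres move power in opposite directions.

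**Substituted Week 12 value.** If Week 12 is below an assay limit L, the Week 16 value needed under the SAP wording is 3L (substituting the limit) or 1.5L (half the limit). At an assumed L of 0.25 that is 0.75 or 0.375 mcg/mL. With the 3.0 condition per serogroup it is max(3.0, 3L) or max(3.0, 1.5L), both equal to 3.0 for any L up to 1.0 mcg/mL.

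**The case against.** The omission may be shorthand. SAP section 4 says that the analysis follows the protocol and that the SAP supplements it. SAP 6.6 cites the protocol, and no intention to remove the condition is stated. That is fair: a deliberate change of endpoint is not shown. The written definitions still conflict, and the conflict has to be resolved whatever its cause.

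Measurable may simply mean that a result exists. The rules are introduced as a way to limit the effect of missing data, and each is conditioned on data being available. This reading is at least as natural as the literal one, and under it the reclassifications in the table disappear. What remains is that a fold-rise from a below-limit Week 12 value needs a number, and SAP 6.6 gives none. The half-limit rule in SAP 6.8.4 is for quantitative summaries of laboratory data and is not linked to the vaccine assays.

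A reader might infer that the measurable rule costs power, or that wrongly scored responders are negligible. The documents support neither. Both conclusions depend on assuming that serogroups drop out independently of response, and the second scenario reverses them. A reader might also infer that the looser SAP rule makes a false non-inferiority claim more likely. That would need titre distributions by arm, which are not given.

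**Conclusion.** The main point holds. SAP 6.6 misstates the protocol's definition of a primary endpoint, and the change is neither declared nor justified. Its direction is certain: it can only add responders, and only through Week 12 IgG below 1.0 mcg/mL. The undefined word is a real but secondary gap. On the literal reading it can move subjects either way or leave them without a result.

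Neither effect can be sized. The documents give no assay limit, no titre distribution, no share of below-limit results and no correlation between serogroups. No power loss and no bound on either kind of misclassification is claimed. The two scenarios show only that the sign is open. The case rests on fidelity to the protocol's endpoint and on a derivation that two programmers would carry out alike.

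**What to change.** Before unblinding:

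1. Restore the IgG ≥3.0 mcg/mL condition in SAP 6.6 and state that it applies to each serogroup. The protocol does not say so, and the sponsor must confirm it. Otherwise, declare and justify the change as protocol 14.3.10 requires, and report the protocol definition as a sensitivity analysis.
2. State that below-limit results count as data. A below-limit Week 16 result is a non-response for that serogroup. A below-limit Week 12 result enters the fold-rise at a value pre-specified from the assay limit. With the 3.0 condition applied per serogroup, the limit and half the limit classify subjects alike for any limit up to 1.0 mcg/mL, so state each serogroup's limit.
3. Apply 3 of 4 whenever all four serogroups were assayed at both visits. Keep the reduced-antigen rules for absent samples or failed assays.

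The cost is SAP wording and derivation code, with no new data. The downside is that restoring the 3.0 condition can only leave the response rate equal to or lower than under the current SAP wording. It is, however, the endpoint as the protocol defines it, for which protocol 14.1 assumes 80%.

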## 14 Statistical methods

### 14.1 Sample size

A total of 200 subjects will be randomised 1:1 to tralokinumab or placebo to ensure that a sufficient number of subjects complete the trial and fulfil the definition of the per protocol set which is considered the primary analysis set for establishing non-inferiority between tralokinumab and placebo with regard to immune responses to vaccines.

With 200 subjects in the FAS and 160 subjects anticipated in the per protocol set, the trial will provide 98% power to establish non-inferiority with regard to positive anti-tetanus response based on a one-sided significance level of 2.5%, assuming a response rate of 80% in both arms and a non-inferiority margin of -25%. Assuming a positive anti-meningococcal response rate of 80% in both arms, an IGA 0/1 response rate of 30% (tralokinumab) versus 10% (placebo), and an EASI75 response rate of 40% (tralokinumab) versus 15% (placebo), the trial will provide approximately 89% power for rejecting all 4 hypotheses related to the primary and secondary endpoints with each hypothesis tested at a one-sided 2.5% significance level. This evaluation is assuming no correlation between the primary and secondary endpoints.

To our knowledge there is no established margin in the literature for showing non-inferiority with regard to immune responses to vaccines and the sample size of previously conducted trials with similar objective varies. In a similar type of trial with dupilumab versus placebo in adults with moderate-to-severe atopic dermatitis (36), a total of 194 subjects was randomised (1:1) to assess vaccine response but no non-inferiority margin was pre-specified. By contrast, in a trial with ixekizumab versus placebo in healthy subjects, a total of 84 subjects were randomised (1:1) and a non-inferiority margin of -40% was pre-specified (ClinicalTrials.gov NCT02543918). Similarly, a non-inferiority margin of -40% was pre-specified in a trial with secukinumab versus placebo in healthy subjects (37).

On the basis of knowledge from previous trials, the proposed sample size and non-inferiority margin of -25% is considered appropriate to assess the primary objective of the trial.

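### The SAP's meningococcal responder cut-off changes with the number of serogroups available, and open patterns are scored in opposite directions

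*SAP*

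**What the plan says.** The protocol defines a positive anti-meningococcal response as if there were one IgG result per subject. SAP 6.6 explains that there are four separate serogroup assays (A, C, W-135 and Y) and sets the subject-level rule:

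- Four available: "If data are available for 4 out of the four antigens, then the subject should be a responder against at least 3 of the antigens".
- Three available: "If data are only available for 3 out of the four antigens, then the subject should be a responder against these 3 antigens".
- Two available: "If data are only available for 2 out of the four antigens, then the subject should be a responder against these 2 antigens".
- One available: "If data are only available for 1 out of the four antigens, then the subject should be a responder against this 1 antigen".

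The stated purpose is "In order to reduce the impact of missing data on the calculation of responders to the meningococcal vaccination". A serogroup counts as available under this condition: "a measurable specific IgG titer against that antigen at both week 12 and week 16 should be available".

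For both primary endpoints, Protocol 14.3.5 says: "Analyses will be based on observed data; hence, missing data will not be imputed". Protocol 14.2 removes from the per protocol set subjects with no vaccine results at Week 16, but not subjects with results for only some serogroups. Neither document has an undetermined category or a sensitivity analysis for partly assayed subjects.

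**The concern.** With complete data one failure is tolerated; with any result missing, none is. The endpoint therefore has a different meaning for each missing-data pattern, and the direction of the distortion is not constant. Take a subject positive on A and C, negative on Y and missing W-135: this is 2 of 3, a non-responder. If the Y result is lost as well, the same subject is 2 of 2, a responder. Losing a negative result should not create a response.

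At stake is the meningococcal non-inferiority comparison, the later of the two primary endpoints in the order listed and a gate to the secondary tests in the hierarchy. Response rates would mix subjects judged on four serogroups with subjects judged on one. If availability differed between arms, the rule itself would move the risk difference.

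**Working it through.** **1. The plan's own figures.** Inputs from Protocol 14.1: 80 per arm in the per protocol set, a margin of -25 points, one-sided 2.5%, 80% tetanus response in both arms, and for this endpoint: "Assuming a positive anti-meningococcal response rate of 80% in both arms". With the unpooled normal approximation, SE = sqrt(2 × 0.8 × 0.2/80) = 0.0632, and power = Φ(0.25/0.0632 − 1.96) = 97.7%, against 98% stated. For all four hypotheses, with 100 per arm for the secondary endpoints: 0.977² × 0.948 (IGA 0/1) × 0.981 (EASI75) = 88.8%, against about 89% stated. Both reproduce and are not in question.

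**2. Which patterns are settled against at least 3 of 4.**

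| Available | Positive | Status of at least 3 of 4 | SAP score |
|---|---|---|---|
| 3 | 3 | settled, yes | responder |
| 3 | 2 | open | non-responder |
| 3 | 0 or 1 | settled, no | non-responder |
| 2 | 2 | open | responder |
| 2 | 1 | open | non-responder |
| 2 | 0 | settled, no | non-responder |
| 1 | 1 | open | responder |
| 1 | 0 | open | non-responder |

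**3. One missing serogroup.** Three of 3 implies at least 3 of 4. So for a result lost irrespective of response, P(3 of 3) cannot exceed P(at least 3 of 4), whatever the correlation. The gap is the probability of 2 positives in the three observed and a positive unseen fourth.

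**4. Size of the step.** The documents give no per-serogroup rate p or correlation, so both are assumed. With independence, the four rules give 4p³ − 3p⁴, p³, p² and p.

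| Assumption | 4 available | 3 | 2 | 1 |
|---|---|---|---|---|
| p = 0.70, independent | 65.2% | 34.3% | 49.0% | 70.0% |
| p = 0.80, independent | 81.9% | 51.2% | 64.0% | 80.0% |
| p = 0.90, independent | 94.8% | 72.9% | 81.0% | 90.0% |
| p = 0.80, beta-binomial correlation 0.5 | 77.3% | 67.2% | 72.0% | 80.0% |

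If the four-serogroup rate is instead fixed at the protocol's 80% (p = 0.788 under independence), P(3 of 3) is 48.9%. In an equicorrelated normal model it is 58.4%, 63.7%, 68.8% and 74.4% at latent correlations 0.3, 0.5, 0.7 and 0.9.

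Only the step from four to three is harder in every case. Under independence, 1 of 1 is easier than at least 3 of 4 when p is below 0.768, and 2 of 2 is easier when p is below 1/3.

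**5. Effect on the comparison.** Suppose 10% of an arm lacks exactly one serogroup, with independence and 80% on the four-serogroup target. That arm's rate becomes 0.9 × 80 + 0.1 × 48.9 = 76.9%.

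- Both arms affected: power 96.3%. With a true difference of -25 points (55% against 80%), one-sided error is 2.7% instead of 2.5%.
- Tralokinumab only: difference -3.1 points, power 92.1%.
- Placebo only: difference +3.1 points. With a true difference of -25 points, one-sided error is 6.3%.

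The one-arm shift is 0.10 × (80 − P(3 of 3)): 3.1, 2.2, 1.6, 1.1 and 0.6 points at latent correlations 0, 0.3, 0.5, 0.7 and 0.9. The beta-binomial case gives 0.10 × (77.3 − 67.2) = 1.0 point.

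**The case against.** The strongest defence is that this is a prespecified available-data rule. The protocol left the four-serogroup derivation unspecified, and the SAP filled the gap before unblinding. Subjects with no Week 16 vaccine data already leave the per protocol set, so only partial missingness matters, and no figure suggests that it is common. The trial is randomised and double-blind, with a central laboratory for the vaccine assays (Protocol Appendix 3D), so no mechanism for unequal missingness is evident. Responses to one conjugate vaccine with one carrier protein are unlikely to be independent, so the 3-point figure is an extreme. All of this stands, and it limits the size of the point. It does not make the cut-off coherent across patterns.

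A reader might infer that the rule breaches the protocol's statement that missing primary-endpoint data are not imputed. The documents do not support this. SAP 6.6 fills in no serogroup value; it classifies subjects on what was observed, and Protocol 14.3.5 does not say how four assays become one response.

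A reader might also infer that every partly assayed subject is misjudged. That is too broad: 3 of 3, 0 or 1 of 3, and 0 of 2 are settled and scored correctly.

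Finally, the availability condition might be read as making a titre below the assay limit count as missing, which would let poor responders drop out of the denominator. SAP 6.6 does not say so. The half-limit convention in SAP 6.8.4 concerns quantitative summaries of laboratory values. This is a gap in definition, not a shown bias.

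**Conclusion.** The point holds as an inconsistency in the derivation of a primary endpoint. The responder cut-off depends on how many serogroups happen to be available, response is harder with one missing under any correlation, and five open patterns are scored as definite in both directions. These statements follow from the SAP text alone.

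The size rests on assumed per-serogroup rates, correlation and missingness. With low and equal partial missingness the effect is small: at 10% in both arms, 1.4 points of power. With 10% in one arm only, the rule moves the difference by about 1 to 3 points, and by less than 1 at very high correlation. Nothing in the documents shows that such an imbalance is expected, so they do not support reading this as a threat to the trial's conclusion or as an error in the stated power. It should be corrected because the correction is cheap and the endpoint is primary.

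**What to change.** In SAP 6.6, use one cut-off, at least 3 of 4, and base the primary meningococcal derivation on subjects with all four serogroups available. Inclusion then does not depend on the observed response, in line with the protocol's observed-data analysis. For that to hold, the SAP should also state how a titre below the assay limit is treated.

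Add, as sensitivity analyses:

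- the current available-antigen rule;
- best-case and worst-case bounds, with settled patterns scored as settled and open patterns scored both ways by arm, including open tralokinumab subjects as non-responders with open placebo subjects as responders.

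Tabulate the number of serogroups available by arm.

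A tempting alternative is to score responders at 3 or more positives, non-responders at 2 or more negatives, and everyone else as missing. It should not be the primary rule. With two serogroups available, the only pattern that it can classify is 0 of 2, so every such subject kept is a non-responder by construction.

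The cost is SAP wording, one derivation and some precision. If 10% of each arm were incomplete, 72 per arm would remain, and power would be Φ(0.25/sqrt(2 × 0.8 × 0.2/72) − 1.96) = Φ(1.79) = 96.3%, the same as under the current rule with one serogroup missing in 10% of both arms. The gain is an endpoint with one meaning, not power.
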